# **11.2.** Study Procedures

#### **11.2.1.** Physical Examination

A Comprehensive Physical Examination will be conducted at baseline. The exam will include the following organ systems: Constitutional; Eyes; Ears, Nose, Mouth and Throat; Neck; Respiratory; Cardiovascular; Gastrointestinal (abdomen); Lymphatic; Musculoskeletal; Skin; Neurologic; and Psychiatric. Subjects should be carefully screened at baseline for depression and suicide attempts or ideations. If there are indications or a history of depression is strongly recommended that these patients be closely followed together with behavioral health or psychiatric medical support. Subjects with an established diagnosis of depression or reported previous suicide attempts or suicidal ideations should not be enrolled on this protocol; the risks and benefits of being treated with the study drug should be weighed very carefully in consultation with behavioral health or psychiatry.

A Basic Physical Examination will be performed at each subject visit, the presence of lymphadenopathy, edema, rash or pain will be recorded. The subject's psychological status will be evaluated as part of the physical examination in each study visit. Information on exam will be documented in the medical record and on CRF/eCRF.

Subjects will be evaluated for response by laboratory blood tests, radiological, pathological and immunological tests, as well as by performance status in order to determine if there is evidence of disease progression. Subjects that have clinically deteriorated and do not show evidence of response, in the judgment of the PI, will be discontinued on further experimental treatment and advised of alternative treatment options.

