# 7. STUDY OBJECTIVES

#### 7.1. PRIMARY OBJECTIVES

- 1. To determine the safety of AlloStim® combined with cryoablation vs AlloStim® alone.
- 2. Determine the schedule that provides the greatest efficacy and least adverse events

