# 9. STUDY ENDPOINTS

# 9.1.PRIMARY ENDPOINT

Safety will be the primary endpoint of this study and will be evaluated on the basis of the following parameters:

- Physical examination and vital signs (temperature, blood pressure, pulse rate, respiratory rate, and blood oxygen saturation).
- Clinical laboratory profile (complete blood count (CBC), comprehensive metabolic panel (CMP), C-reactive protein (CRP), coagulation factors and autoimmune parameters.
- Adverse events according to the National Cancer Institute (NCI) Terminology Criteria for Adverse Events (CTCAE) version 4.03 (refer to section 15 for AE/SAE management and reporting):

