#### **DESCRIPTION OF STUDY VISITS** 12.

The following tables summarize all planned assessments, tests, and treatments scheduled to occur as part of this study, including pretreatment evaluations, end of therapy assessments, and follow-up. These assessments will be conducted at the PI clinic and a Sponsor-designated radiology center (imaging, cryoablation and biopsy). Some deviations in the schedule of assessments are allowed as indicated in protocol deviation section 12.1.

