### Table 1 Table of Assessments Schedule A-1

| Protocol activity                      | Baseline | ID# 1 | ID# 2 | ID# 3 | Cryoablation | 1# A1 | IV booster #1 | IV booster #2 | CT+biopsy |
|--|----------|-------|-------|-------|--------------|-------|---------------|---------------|-----------|
| Protocol day                           | -14 to-1 | 0     | 7     | 14    | 21           | 28    | 56            | 84            | 91        |
| Informed Consent                       | Х        |       |       |       |              |       |               |               |           |
| Demographics                           | Х        |       |       |       |              |       |               |               |           |
| Inclusion/Exclusion Criteria           | Х        |       |       |       |              |       |               |               |           |
| Medical History                        | Х        |       |       |       |              |       |               |               |           |
| Physical Examination (complete)        | Х        |       |       |       |              |       |               |               |           |
| Physical Examination (brief)           |          | х     | х     | х     |              |       | х             |               |           |
| Vital signs                            | Х        | х     | х     | х     | Х            | х     | х             | х             |           |
| ECOG                                   | Х        |       |       |       |              |       |               |               |           |
| EKG                                    | Х        |       |       |       |              |       |               |               |           |
| CT Scan (head, chest, abdomen, pelvis) | Х        |       |       |       |              |       |               |               |           |
| CT Scan (chest, abdomen, pelvis)       |          |       |       |       |              |       |               |               | х         |
| Cryoablation under US or CT guidance   |          |       |       |       | Х            |       |               |               |           |
| Biopsy                                 | Х        |       |       |       |              |       |               |               | Х         |
| Hematological Profile (CBC)            | Х        |       | х     | х     | Х            | х     | х             | х             | х         |

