Laboratory adverse events should be captured on the AE /SAE CRF/eCRF as appropriate. It is expected that wherever possible, the clinical, rather than the laboratory term, will be used by the reporting investigator.

Clinically significant changes in physical examination findings should also be recorded as AEs.

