#### AEs do not include the following:

- Medical surgical procedures are not AEs (e.g., surgery, endoscopy, tooth extraction, transfusion). The condition that leads to the procedure is an AE if the procedure was not planned at screening visit.
- Overdose of concomitant medication without any signs or symptoms unless the subject is hospitalized for observation.
- Hospitalization for elective surgery planned prior to study (situation where an untoward medical occurrence has not occurred).

AEs will be solicited from physical exam, subject and caregiver/family interview in person or by telephone and laboratory test results. The investigator is to report all directly observed adverse events and all adverse events spontaneously reported by the trial subject or caregiver/family member. Each trial subject will be questioned about adverse events at each clinic visit following initiation of treatment and by telephone at least once a month during the follow-up phase. The question asked should be, "Since your last clinic visit have you had any health problems?", or a similar type of open-ended query.

For all AEs, the investigator must pursue and obtain information adequate both to determine the outcome of the AE, and to assess whether it meets the criteria for classification as a serious adverse event (SAE). For all AEs, sufficient information should be obtained by the investigator to determine the causality of the AE (i.e., investigational product or other illness). The investigator is required to assess causality and indicate that assessment on the CRF/eCRF. Follow-up of the AE is required if the AE persists. Follow-up is required until the event is resolved or stabilized at a level acceptable to the investigator and the Sponsor's medical monitor or his/her designated representative.

AE severity will be recorded and graded according to the National Cancer Institute (NCI) Common Terminology Criteria for Adverse Events (CTCAE) version 4.03 (June 14, 2010) and coded into the database according to the latest version of MedDRA.

 Table 7
 Severity of Adverse Events According to CTCAE (Version 4.03)

| Grade | Description   |
|-------|---|
| 0     | No AE or within normal limits   |
| 1     | Mild; asymptomatic or mild symptoms; clinical or diagnostic observations only; intervention not indicated.  |

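### Section 11.2.1 requires a basic physical exam with a psychological check at every visit, but Table 1 (A-1) omits it on Days 21, 28, 84 and 91, and Table 2 (A-2) only on Day 91

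*Combined protocol and SAP*

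**What the plan says.** Section 11.2.1 gives one rule for both schedules: "A Basic Physical Examination will be performed at each subject visit, the presence of lymphadenopathy, edema, rash or pain will be recorded". It adds that the subject's "psychological status will be evaluated as part of the physical examination in each study visit".

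Section 12 introduces the assessment tables with "The following tables summarize all planned assessments, tests, and treatments scheduled to occur as part of this study". In both tables the relevant row begins "Physical Examination (brief". It is evidently the same exam that the text calls basic, because the only other exam is the comprehensive one at baseline.

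- **Table 1 (A-1):** marked on Days 0, 7, 14 and 56. Blank on Day 21 (cryoablation and intratumoral dose), Day 28 (IV activation dose), Day 84 (second IV booster) and Day 91 (CT and biopsy).
- **Table 2 (A-2):** marked on Days 0, 3, 7, 10, 14, 21, 28, 49 and 77. Blank on Day 91 only.

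Baseline is blank in this row in both tables because the complete exam is marked there, so that is not an omission. No rule was found that says whether the text or the tables govern.

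**The concern.** Text and tables give the site different instructions, and the gap is wider in A-1 than in A-2.

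The exam matters for safety data in three ways:

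- Section 9.1 lists it among the primary endpoint parameters: "Physical examination and vital signs (temperature, blood pressure, pulse rate, respiratory rate, and blood oxygen saturation".
- Section 15 states: "Clinically significant changes in physical examination findings should also be recorded as AEs".
- Section 15.1.3 names it as a source of events: "AEs will be solicited from physical exam, subject and caregiver/family interview in person or by telephone and laboratory test results".

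The signs listed in Section 11.2.1 are not rare with this product. In the earlier 42-subject study summarized in Section 6.6.1, the all-causality tables show lymphadenopathy in 15 subjects (35.71%) and limb edema in 14 (33.33%).

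A primary objective in Section 7.1 is to "Determine the schedule that provides the greatest efficacy and least adverse events". If A-1 subjects are examined less often than A-2 subjects, the chance of recording exam-detected findings differs between the schedules for a reason unrelated to treatment. If A-1 were then favored, the same table would govern up to 25 further subjects in Part 2.

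**Working it through.** The plan states no figure on this point, so there is none to reproduce. The check lines up the brief-exam row with the protocol-day row in each table and counts

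proportion = visits with the exam marked / visits scheduled.

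**Inputs**

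- A-1 dosing days (Table 1): 0, 7, 14, 21, 28, 56, 84, which is 7 visits. Exam marked on 0, 7, 14, 56, which is 4.
- A-2 dosing days (Table 2): 0, 3, 7, 10, 14, 21, 28, 49, 77, which is 9 visits. Exam marked on all 9.
- Day 91 is a further post-baseline visit in both tables, with the exam unmarked in both.

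**Results if a site follows the tables**

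| Count | A-1 | A-2 |
|---|---|---|
| All dosing visits, boosters given | 4/7 = 57% | 9/9 = 100% |
| No boosters (Days 0 to 28) | 3/5 = 60% | 7/7 = 100% |
| Day 21 credited through the pre-sedation evaluation | 5/7 = 71% | 9/9 = 100% |
| A-1 Day 21 left out as a radiology-center day | 4/6 = 67% | 9/9 = 100% |
| All post-baseline visits, including Day 91 | 4/8 = 50% | 9/10 = 90% |
| Both tables corrected to Section 11.2.1 | 8/8 | 10/10 |

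With three subjects per schedule in Part 1, the dosing-visit totals are 3 × 4 = 12 of 3 × 7 = 21 in A-1, against 3 × 9 = 27 of 27 in A-2. If A-1 went forward with 25 more subjects, the unmarked dosing visits would number up to 3 × 25 = 75, or 2 × 25 = 50 without boosters.

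**Is the difference intended?** Two like-for-like pairs suggest not.

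1. Day 28 is the same step in both schedules, a 3 ml IV activation dose. Table 2 marks the exam and Table 1 does not.
2. Within A-1, Days 56 and 84 are both IV boosters of the same dose. The first is marked and the second is not.

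Other marks that the text requires are missing too. Section 11.2.4 calls for a Day 21 biopsy in A-1 and a Day 91 CT for all subjects, but Table 1 has no Day 21 biopsy mark and Table 2 has no Day 91 CT mark. Omission is the likelier explanation.

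**Is it a reading artifact?** The A-1 row has four marks for eight post-baseline columns, so no column shift could fill it. The A-1 vital-signs row is marked at all seven dosing visits, so the columns line up. Neither fact rules out individual marks lost when the PDF was read.

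**The case against.** The strongest objection is that the tables may have been damaged in reading. Some column headers are garbled, the asterisks in the row labels have no footnote text, and the post-baseline CT row in Table 2 has no marks at all. Column alignment rules out shifted marks but not dropped ones. This stands as a residual doubt and is why confidence is medium. It should be settled against the source PDF.

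Second, Section 11.2.1 is clear, the tables only summarize, and Section 15.5 binds the investigator to the procedures the protocol requires. A site that follows the text has no gap. That is true, but Section 12 presents the tables as covering all planned assessments, so a site could reasonably schedule from them.

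Third, other observation is substantial. Adverse events are marked at every post-baseline visit in both tables. Section 8 requires acute dose-limiting toxicity to be assessed within 48 hours of priming, vaccination and activation doses, whatever the exam row shows. Vital signs are followed for 2 hours after IV and intratumoral doses.

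On Day 21, Section 6.1.2 requires at least 2 hours of observation. Appendix 1 adds a history-and-physical-based evaluation before the procedure, and orientation, pain and discharge checks after it. That evaluation is written for subjects who need IV conscious sedation, and local sedation alone is allowed. None of these Day 21 provisions names rash, edema or lymphadenopathy, and none of them covers Days 28 or 84.

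Fourth, the ratios count marks in a table, not missed events, and the comparison is three against three with descriptive statistics. That is correct and limits the weight of the point. Day 91 is blank in both tables and adds no asymmetry between schedules.

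**Conclusion.** The concern holds as a minor inconsistency, with medium confidence. The text requires the exam and the psychological check at every visit. Table 1 leaves out four post-baseline visits, three of them dosing visits, and Table 2 leaves out one, which is not a dosing visit.

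The size, 4 of 7 dosing visits in A-1 against 9 of 9 in A-2, rests on three assumptions: the site follows the tables, the boosters are given, and the extracted rows match the source. Dropping the boosters, crediting Day 21 or leaving it out moves the A-1 figure only between 57% and 71%.

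Any effect is confined to findings that depend on the exam. Its net direction on the comparison of schedules is not established.

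**What to change.** Mark the brief exam, with the psychological check, on Days 21 (before the procedure), 28, 84 and 91 in Table 1 and on Day 91 in Table 2. If fewer exams are intended, revise Section 11.2.1 instead and apply one rule to both schedules.

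The cost is five table marks, for an exam the text already requires at visits that already take place. Because Days 21 and 91 involve the radiology center, the plan should also say who performs the exam there and where the form is kept. For sedated subjects on Day 21, the pre-procedure evaluation can supply part of it.

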#### **11.2.2.** Monitoring Vital Signs

After each ID injection of study drug, the vital signs will be monitored with real-time monitoring equipment for heart rate, respiration rate, blood pressure, temperature, and pulse oximetry. Values will be recorded every 15 minutes for one hour on a provided form. If vital signs are stable, the subject can be discharged after 1 hour. Otherwise, the subject should continue to be observed until stable.

After each IV infusion and IT injection of study drug the vital signs will be monitored with realtime monitoring equipment for heart rate, respiration rate, blood pressure, temperature, and pulse oximetry. Values will be recorded every 15 minutes prior, during and for 2 hours following the infusion. All changes in vital signs from baseline during and after the infusion will be recorded in the treatment notes. If vital signs are stable, the subject can be discharged after 2 hours. Otherwise, the subject should continue to be observed until stable.

# **11.2.3.** Laboratory tests

All scheduled and unscheduled laboratory assessments will be analyzed by the local laboratory.

Hematology Profile – includes a complete blood count (CBC) with differential.

Chemistry Profile - includes sodium, potassium, chloride, calcium, BUN, creatinine, calcium, total protein, albumin, Aspartate transaminase (AST), Alanine transaminase (ALT), alkaline phosphatase, total bilirubin and direct bilirubin.

Inflammation Marker - C-reactive protein (CRP), erythrocyte sedimentation rate, total IgG and IgM, and lipase

Coagulation Profile - includes INR or prothrombin time (PT) if available (whichever is selected should be followed throughout) and partial thromboplastin time (PTT).

Autoimmune Profile - includes complement C3, anti-DNA Ab, anti-nuclear Ab (ANA), antimitrochondrial Ab(AMA), anti-smooth muscle Ab (SMA), liver/kidney/microsomal Ab (LKM).

Pregnancy Test – for women of childbearing potential, a pregnancy test (serum or urine) is required pretreatment. Minimum sensitivity 25 IU/L or equivalent units of β-human chorionic gonadotropin (β-HCG).

#### 11.2.4. Tumor Assessment

CT scan of the Head/Chest/Abdomen/Pelvis with and without contrast (if tolerated) will be conducted at baseline and Day 91. All subjects accrued in schedule A-1 will also be evaluated at baseline to confirm they have a liver lesion that can be readily visualized and safely approached percutaneously for cryoablation.

Subjects will undergo mandatory tumor biopsies of at least one selected target lesion (not lesion targeted for ablation) at baseline, during intratumoral injections (day 21 Schedule A1 and on Day 91.

The intratumoral procedures use a trocar that will have already been inserted into the tumor to conduct the intratumoral injection and thus these biopsies will not add an additional invasional procedure.

In order to obtain information on the longitudinal changes in the immune cell patterns of tumors as well changes in tumor size, biopsies will be collected for subjects who consented under a separate inform consent. These additional biopsies will be conducted only if subjects separately consent. Failure to consent for the intermediary biopsy procedures will not disqualify subjects.

The biopsies material should be placed in containers supplied by the Sponsor. The samples should be labeled with protocol number, subject study ID, date of birth, date of sample collection and sample time point (protocol day). The containers should be kept at room temperature (RT) and delivered to Sponsor's histology lab within 24h of collection to:

> [name], MD (Pathologist): Immunovative Clinical Research, Inc., [name]

A biopsy is useful because subjects on immunotherapy can present with "flared" lesions that appear to be larger on CT scan, but may not necessarily represent disease progression. Increase in size can be due to immune cell infiltration, edema, coagulative necrosis and/or fibrotic changes rather than tumor growth. In addition, subjects may present with new lesions which may not necessarily represent progressive disease, but may instead represent immune reactivity to microscopic disease previously not visible. The initial appearance of progressive disease may occur during immunologic therapy for at least two reasons. First, immunotherapy may induce lymphocytic tumor infiltration and inflammation of the tumor, and the associated increase in tumor diameter is then scored as progression on radiographic imaging (i.e. 'tumor flare'). Second, the appearance of new lesions or growth of primary lesions may occur after immunotherapy has been administered, since the process of immune activation is complex and delayed. During this period of activation, the tumor may be able to transiently grow even when effective therapy is priming the immune system to eventually respond.

Immunotherapy may induce responses with a variety of kinetic patterns. Some tumors may respond rapidly, meeting criteria for a RECIST response. Other tumors may respond late in the course of treatment, wherein standard 2- and 3-month evaluations of these patients would classify them as non-responders. Some tumors may actually increase in diameter before eventually regressing. Using RECIST criteria, such patients would be classified as having disease progression and generally would be removed from a trial before late response might be documented [84]. Because of the unique patterns of clinical response that arise with immune-modulating therapies, alternative clinical trial design and end points are necessary to properly evaluate these agents.

For these reasons, irRC and longitudinal tumor biopsies are used in this study in order to distinguish whether changes in the radiographic appearance of tumors correlates with progression or tumor flare, while overall survival is used as the primary endpoint due to the unreliability of RECIST as a method to evaluate response to immunotherapy. The experimental endpoint of seroconversion to IL-12 positivity was found in an earlier Phase I/II clinical trial to correlate with survival. Therefore, radiological, pathological and immunological endpoints will be used for assessment of tumor response.

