#### **Radiology Assessment:**

All subjects will undergo a CT scan of the head, chest, abdomen and pelvis with and without contrast (contrast can be withheld if medically indicated) at baseline and at Day 91 at same time as biopsy.

As it is difficult to determine if subjects are responding or progressing after immunotherapy by standard radiological methods and RECIST criteria, the analysis of the CT scans is conducted as an experimental end-point. It is known that after immunotherapy that subjects can develop new lesions, experience lymphadenopathy and interval size increases in tumors. These changes would normally be documented as progression. However, in immunotherapy, the changes could represent "pseudo-progression". In some cases, the changes could indicate actual progression, but a response can still occur months after immunotherapy. Other times, immunotherapy can cause a stable disease condition that results in increased survival.

The changes in the images will be analyzed by RECIST and other accepted and novel experimental methods in order to retrospectively determine a method that best correlates with survival outcomes. The CT scans are scheduled on the same day as biopsy procedures in order to correlate the radiological images with pathological response. It is believed that patterns of necrosis, fibrosis and immune cell infiltration patterns with HU numbers on the radiographic images may provide correlates that could distinguish immune response from progression or be predictive of a survival response. Radiographic images can be reviewed by the site radiologists according to established methods. At the discretion of the PI, select subjects may be further evaluated by MRI or PET in order to attempt to distinguish between radiological "pseudo-progression" due to an immune response and actual progression.

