## Histopathology Assessment:

Subjects will undergo mandatory tumor biopsies of a target lesion at baseline, during intratumoral injections (Schedule A-1) and at Day 91. The intratumoral procedures use a trocar that will have already been inserted into the tumor to conduct the intratumoral injection and thus these biopsies will not add an additional interventional procedure on day 21 Schedule A-1

Additional biopsies will be conducted only if subjects separately consent. Failure to consent for the additional biopsy procedures will not disqualify subjects.

The harvested tissue will be prepared in paraffin blocks and read centrally by a pathologist appointed by the Sponsor. The amount of tumor burden estimated from the pathological evaluation will be compared with the amount of burden shown on the CT images. The amount and type of immune cell infiltration (immunohistochemical analysis), existence of coagulative necrosis, necrotic tumor and fibrosis will also be documented and correlated to the radiological images.

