# 11.2.7. Th1/Th2 Intracellular Staining

AlloStim® priming is designed to increase the number of Th1 cells in circulation. Since IFN-y is a prototypic marker of Th1 cells and IL-4 is a prototypic marker of Th2 cells, the Th1/Th2 balance can be detected by activating T-cells and measuring the expression of IFN- $\gamma$  and IL-4. Th1/Th2 analysis requires ~50 ml of whole blood in blood tubes provided by the sponsor. The PBMC will be isolated from whole blood following the instructions provided by the Sponsor. Briefly, the whole blood tubes should be centrifuged at 1500 rcf for 15 minutes and whitish layer to be collected into new pre-labeled tube. After the cell counting, the separated PBMC will be washed by centrifugation 8 minutes at 402 rcf, and re-suspended in freezing medium to final concentration of  $10 \times 10^6$ /ml. The suspended cells will be aliquoted to  $10^7$ PBMC/vial. All PBMC samples should be labeled with subject study ID, protocol number, protocol day, date and time of collection. PBMC samples should be frozen and stored at -80°C or below until shipping. All PBMC samples will be shipped on a dry ice or in a liquid nitrogen dry shipper via overnight courier to:

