#### **17.10. DATA CAPTURE**

#### 17.10.1. Case Report Forms

The CRF is an integral part of the study and subsequent reports. The CRF must be kept current to reflect subject status during the course of the study. Only the subject number and an alpha code will be used to identify the subject.

After obtaining written source document information from each subject at each visit, the site will enter the data onto a paper CRF or directly into an internet –based data collection system (as described under section 11.50.2; Electronic Data Capture).

Source documents are where subject data are recorded and documented for the first time. They include, but are not limited to hospital records, clinical and office charts, laboratory notes, evaluation checklists, pharmacy dispensing records, recorded data from automated instruments, copies of transcriptions that are certified after verification as being accurate and records kept at the pharmacy, laboratories, and other departments involved in a clinical trial.

Source documents that are required to verify the validity and completeness of data transcribed on the CRFs must never be obliterated or destroyed.

The investigator will maintain a Delegation of Authority Page to document all persons authorized to make entries and/or corrections on CRFs. The CRF should be reviewed, signed, and dated by investigator.

In case of paper CRF, all CRFs should be completed in a neat, legible manner to ensure accurate interpretation of data. Black ink is required to ensure clarity of reproduced CRF copies. When making changes or corrections, original entries will be crossed out with a single line, and the changes will be initialed and dated. DO NOT ERASE, OVERWRITE OR USE CORRECTION FLUID ON THE ORIGINAL CRF ENTRY.

According to the GCP guidelines, the investigator (or designee) will check the CRF entries against the source documents, except for the pre-identified source data directly recorded in the CRF.

The following table identifies what are source vs. CRF data in this study:

| Type of Data   | Source/CRF  | Comment   |
|--|---|---|
| Informed consent   | Source documents  | Signature date is captured on CRF   |
| Demographics   | Source documents and CRF                                  |   |
| Inclusion/Exclusion  | Source documents and                                      |   |
| Criteria   | CRF   |   |
| Medical History (incl.   | Source documents and                                      |   |

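### Biopsy labels show the Sponsor's central pathologist the time point, so judgement-based pathology scores are read unmasked and expectation can bias the change from baseline

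*Combined protocol and SAP*

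**What the plan says.** Section 11.2.4 fixes the label on each biopsy: "The samples should be labeled with protocol number, subject study ID, date of birth, date of sample collection and sample time point (protocol day". The material is to be "delivered to Sponsor's histology lab within 24h of collection", and the addressee there is a pathologist. Under Histopathology Assessment in the Abstract, the tissue is "read centrally by a pathologist appointed by the Sponsor". The features recorded are estimated tumor burden, amount and type of immune infiltrate, coagulative necrosis, necrotic tumor and fibrosis.

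The use of the scores is also stated there: "The amount of tumor burden estimated from the pathological evaluation will be compared with the amount of burden shown on the CT images". Under Radiology Assessment, "The CT scans are scheduled on the same day as biopsy procedures in order to correlate the radiological images with pathological response", and "Radiographic images can be reviewed by the site radiologists according to established methods".

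Section 8 describes a single-center, open-label study. Section 9.2 makes the correlation of RECIST, pathological response and immune response with overall survival an exploratory endpoint, and Section 16.1.6 limits its analysis to descriptive statistics by schedule. No section provides for masking the pathologist, re-coding samples, random reading order or a second reader.

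**The concern.** These features are graded by eye. A reader who knows that a slide is from Day 91 also knows what the protocol expects to see there: Section 11.2.4 explains at length that lesions enlarged on CT may contain infiltrate, edema, necrosis or fibrosis and not growing tumor. Uncertain fields can then be read toward that expectation. There is no untreated control group, so the within-subject change carries much of the pathological evidence, and that is the comparison the label unmasks.

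The scores matter although the endpoint is exploratory. Section 11.2.4 lists pathological endpoints among those used to assess tumor response. Section 9.2 uses serial biopsies to judge whether RECIST can predict survival under this therapy. Section 8 advances a schedule to Part 2 on safety and efficacy data from Part 1. The Abstract's primary objective includes anti-tumor effect, and Section 7.1 seeks the schedule with the greatest efficacy.

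**Working it through.** **What the reader can know**

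| Item | Visible to the reader? | Basis |
|---|---|---|
| Time point and collection date | Yes, on the label | 11.2.4 |
| Schedule | Sometimes. The text gives a Day 21 biopsy only in A-1, and Table 2 marks a Day 14 biopsy in A-2 | Abstract, 11.2.4, Table 2 |
| CT result | Not stated either way | Silence in the Abstract and 11.2.4 |

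The first row follows directly from the plan. The last is inference from silence.

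**Size of the possible bias**

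The plan gives no alpha, effect size or SD for pathology, so there is no planned figure to reproduce. What follows is an illustration with assumed inputs.

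- Let d be the reader's shift of post-treatment scores, in SDs of the paired change, with a true mean change of zero. Assume d = 0.2, 0.3 or 0.5.
- In descriptive terms the result is simple: the reported mean change is d SDs instead of 0. A larger sample does not reduce it.
- To put that on a familiar scale, take a two-sided 5% paired t-test with n pairs. The rejection rate is P(|T| > t(0.975, n − 1)), where T is noncentral t with n − 1 degrees of freedom and noncentrality d√n.

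Choice of n:

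- n = 28 is the full favored schedule without cohort expansion: 3 from Part 1 plus up to 25 from Part 2 (Section 8).
- n = 20 allows for deaths before Day 91. With exponential survival and a median of 6.5 months, 28 × 0.5^(3/6.5) = 20.3. The 6.5 months is the figure the protocol cites for KRAS-mutant patients given TAS-102. It is borrowed from another drug and a subset, so n = 20 is only a plausible middle value.
- n = 10 allows for further loss: subjects dropped under Section 14.6, discontinued under 11.2.1, or declining serial biopsies as 17.1 permits.

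| n | t(0.975, n − 1) | d = 0.2: d√n, rejects | d = 0.3: d√n, rejects | d = 0.5: d√n, rejects |
|---|---|---|---|---|
| 10 | 2.262 | 0.632, 9% | 0.949, 14% | 1.581, 29% |
| 20 | 2.093 | 0.894, 14% | 1.342, 25% | 2.236, 56% |
| 28 | 2.052 | 1.058, 18% | 1.587, 33% | 2.646, 72% |

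If masked reading removed the shift (d = 0), every cell would return to 5%.

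**Can the time point be masked?**

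Largely, but not always. Section 11.2.4 says the biopsied target lesion is not the one chosen for ablation. Appendix 1 makes that a preference and allows the ablation lesion to be biopsied, before ablation, when there is no second lesion. In those subjects the Day 91 sample may come from ablated and injected tissue, and its appearance may give it away.

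**The case against.** The strongest reply is that the endpoint is exploratory, its analysis is descriptive, and the primary endpoint is safety. That stands as a limit. A reader might infer from the table that a planned test has an inflated error rate. The documents specify no such test, so the percentages only express the bias on a familiar scale. The reply does not remove the problem, because a reader shift distorts a descriptive mean or correlation just as it distorts a test.

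A second reply is that a CT-driven read is conjecture: biopsies go to the Sponsor's lab, CT can be read by site radiologists, and comparing the two describes an analysis, not reading with the scan in hand. This stands. The plan fails to exclude such knowledge, but does not say it occurs.

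A reader might also infer that every such error favours the drug. The documents do not support that. Pathology scores pulled toward CT would raise agreement and make RECIST look more valid, whereas Sections 9.2 and 11.2.4 argue that RECIST misleads in immunotherapy.

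Two further inferences go too far. The blood samples carry similar labels ("All PBMC samples should be labeled with subject study ID, protocol number, protocol day, date and time of collection" in Section 11.2.7), but nothing in the documents shows that the cytokine or Th1/Th2 results depend on a reader's judgement. Nor can the Day 21 sample in A-1 be assumed unmaskable because of fresh ablation necrosis: Appendix 1 places the needle biopsy before the cryoprobe is inserted.

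Finally, labels serve sample tracking, and pathology has uses during the study: judging response and deterioration (11.2.1) and separating exacerbation from lack of efficacy (Section 15). Both are fair points, and the fix has to leave them intact.

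**Conclusion.** The point holds for the time point. As written, the plan gives the Sponsor-appointed reader the protocol day and date of every biopsy and asks for judgement-based scores with no masking, so expectation can bias the change from baseline and its later uses. Bias is possible, not shown. Its size and direction are unknown, and the 9% to 72% range rests entirely on assumed shifts of 0.2 to 0.5 SD and assumed numbers of pairs from 10 to 28. For CT knowledge the point holds only as something the plan does not prevent, with no settled direction. The primary safety analysis is not called into question. This is an inexpensive improvement that should be made before the pathology scores are used for response, correlation or schedule choice.

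A separate small matter is date of birth on the label. Section 17.10.1 says "Only the subject number and an alpha code will be used to identify the subject", but that section governs case report forms. The passage to reconcile with 11.2.4 is the general confidentiality rule in 17.7, which restricts identification to initials and a unique number.

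**What to change.** In Section 11.2.4:

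- Keep protocol day, dates and identifiers on the requisition and container for tracking. Have lab staff other than the reading pathologist receive the sample and put a random code on blocks and slides.
- For the research score, have the same central pathologist read each subject's stored slides in random order once the last available biopsy is in (Day 91, or the last sample if Day 91 is not reached), without time point, schedule, CT, immune or survival data.
- Lock the scores before merging them with CT, and score CT for this comparison without access to them.
- Let any prompt pathology result needed under 11.2.1 or Section 15 continue as an ordinary clinical read, preferably by someone other than the research reader, and do not use it as the research score.
- State that masking may fail where the biopsied lesion is the ablated one, and flag those samples.
- Reconcile date of birth on the label with 17.7.

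The cost is a code list, a short lab instruction and a re-coding step, with no extra biopsy or visit. Research scores arrive later, and recall remains possible if one pathologist does both reads.
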